11.16 Asthma exacerbation assessment

An Asthma Action Plan (Section 11.19) will be given to the subjects and parents/caregivers to provide guidance to effectively manage the subject's symptoms, as recommended by clinical practice guidelines. Subjects will be trained in their Asthma Action Plan by the investigator or designee.

According to the Asthma Action Plan subjects must contact the investigator when asthma symptoms increase or in cases with reduction in lung function. The investigator or designee will fill in the appropriate treatment for the subjects in the Asthma Action Plan.

Subjects will continue with a constant dose of low dose ICS plus LABA or medium/high dose ICS with or without LABA throughout the trial.

If a subject presents with worsening of asthma symptoms, investigator or designee should always evaluate if the subject requires treatment at emergency room. If emergency room visit is not required initial treatment can be either:

- Doubling of ICS dose compared to background treatment for 2 weeks, or
- Systemic corticosteroids for treatment of asthma symptoms for at least 3 days

For the doubling of ICS dose a separate inhaler with ICS will be provided by ALK as part of the asthma rescue medication. Subjects may also double their ICS dose by using their background medication. Subjects that receive high dose ICS as background treatment are not allowed to double the dose of ICS. Please note that local regulations and SmPCs or USPI must be followed. In case of an asthma exacerbation requiring systemic corticosteroids, the subjects should be treated with OCS in the form of Prednisolone/Prednisone tablets. Dosing regimen should follow recommendations by GINA guideline (GINA Executive Committee 2017), NIH guidelines (National Heart Lung and Blood Institute 2007) or national guidelines (Reddel et al. 2009). See Section 8.3.

The use of LTRA is permitted for continued use only but will not be provided by ALK.

If a subject has 2 severe asthma exacerbations within 12 consecutive months or is hospitalised due to asthma requiring treatment with systemic corticosteroids the subject must be discontinued from the IMP treatment.

Each severe asthma exacerbation must be separated by >7 days from the discontinuation of OCS to be considered an individual event (Lanier et al. 2009).

Each clinically relevant asthma exacerbation must be separated by >7 days from the discontinuation of additional ICS or OCS to be considered an individual event.

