14.5 Database lock

When the database has been declared to be complete and accurate, the database will be locked, access for CRAs and non-sponsor staff/persons will be revoked and data may be unblinded.

If changes to trial data become necessary after database lock this must be performed according to the current ALK standard operating procedures (SOP).

A data archive for the site subject data files are produced and sent to the site. The investigator must sign and date the data archive approval form and send it back to the sponsor.

15 Statistical methods

Statistical analyses will be carried out by ALK Biometrics Department.

If nothing else is mentioned, all the statistical tests described in this section use a significance level of 5% and all tests and confidence intervals are two-sided. The null hypothesis is the hypothesis of no difference and the alternative to the null hypothesis is the hypothesis of a difference.

Descriptive statistics for numerical variables includes summary tables displaying mean, SD, median, 5%-quantile, 25%-quantile, 75%-quantile, 95%-quantile, minimum and maximum. Descriptive statistics for categorical variables includes frequencies tables that display numbers and percentage.

Before database lock, a separate statistical analysis plan (SAP) detailing the specifications given below will be prepared and agreed upon.

Any changes in the statistical methods compared to the final SAP will be documented in the ICTR. Post-hoc analyses, if any, will be clearly marked.

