15.1 Sample size and power considerations

The primary endpoint is the annualised rate of clinically relevant asthma exacerbations during the efficacy evaluation period (period 4). The rate of clinically relevant asthma exacerbations will be analysed using a negative binomial regression model.

From (Lanier et al. 2009) the rate of clinically relevant asthma exacerbations is expected to be approximately 1.4 exacerbations per subject per year. Over a period of 24 weeks the number of clinically relevant asthma exacerbation in the placebo group were 0.64 per subject (\sim 0.64*52/24 =1.4 per subject per year).

Power calculation are both performed based on the negative binomial distribution assuming overdispersion and based on the poisson distribution when assuming no overdispersion. Overdispersion means that some subjects will tend to have more exacerbations than others. The dispersion parameter in the negative binominal distribution is assumed to be k=0.7 (Pavord et al. 2012). When there is no overdispersion (k->0) the negative binominal distribution will become a poisson distribution.

Table 13 displays the sample size calculations for different values of the treatment effect expressed as the reduction in exacerbation rates for active treatment compared to placebo (100%*(PLB-ACT/PLB)). The power is set to 90% and sample size calculations are performed using a close formula for the negative binomial regression model (Keene et al. 2007):

$$N = \left\{ \frac{z_{1-\beta} + z_{1-\alpha/2}}{\log (\mu_1/\mu_2)} \right\}^2 \times \left\{ \frac{\mu_1 + \mu_2}{\mu_1\mu_2} + 2k \right\}$$

where N is the number of subject per treatment arm, μ_1 is the rate per subject in the given time interval for the placebo group, μ_2 is the rate per subject in the given time interval for the active group, $1 - \beta$ is the power, alpha is the level of significance and k is the dispersion parameter.

Table 13 Power	calculation
----------------	-------------

Power	Alpha	Time for efficacy assessment (weeks)	Rate PLB	Reduction (%) 100%*(PLB- ACT)/PLB)	μ ₁	μ2	k	N per arm (NB*)	N per arm (POIS)	
	0.05	34			0.91	0.63		334	219	
	0.05	52		30%	1.39	0.97		259	143	
	0.05	86			2.29	1.61		202	87	
0.9	0.05	34	1.4	25%	0.91	0.68	0.7	501	324	
	0.05	52			25%	1.39	1.04		389	212
	0.05	86			2.29	1.72		306	128	
	0.05	34			0.91	0.73		814	519	
	0.05	52			20%	1.39	1.11		635	339
	0.05	86			2.29	1.83		500	205	

PLB: placebo, ACT: active, NB: negative binominal, POIS: poisson distribution.

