### 1.1.5 Primary endpoint

The primary endpoint of the trial is the annualised rate of clinically relevant asthma exacerbations calculated as the number of exacerbation events per year per subject during the efficacy evaluation period (period 4).

A clinically relevant asthma exacerbation must be medically confirmed and is defined as asthma worsening leading to at least 1 of the following criteria:

- Doubling of ICS dose compared to background treatment
- Systemic corticosteroids for treatment of asthma symptoms for at least 3 days
- Emergency room visit due to asthma, requiring systemic corticosteroids
- Hospitalisation for more than 12 hours due to asthma, requiring treatment with systemic corticosteroids

Type of document	Date:	11-Aug-2022	
Document ID	Version:	4.0	
	Status:	Final	
INTERNAL USE	Page:	15 of 79	

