### 1.2.3 Randomisation

The randomisation list has been generated by a trial-independent statistician and will not be accessible to trial personnel involved in the conduct of the trial, until the database has been locked.

At least 45% of the subjects will be 5-11 years of age at the time of randomisation in accordance with the recommendation of EMA/PDCO standard paediatric investigation plan for allergen products for specific immunotherapy **(EMA and PDCO 2015)**. No other stratification will be used in this trial.

When a subject is randomised, a unique number is assigned for the first dispensing of IMP.

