### 4.2.3 Main analytical approach

The primary endpoint, based on both the primary and secondary estimand, will be compared between treatment groups using the hypothetical estimand for the FAS population using either the DPS1 or DPS2, i.e. subjects for whom the primary endpoint is missing due to discontinuation of treatment prior to period 4 will not contribute to the analysis. This approach of using observed data only (an observed case analysis), implicitly assumes that observations are missing completely at random (MCAR), i.e. had the subjects continued treatment into the efficacy assessment period (period 4), they would have experienced the same treatment effect as subjects from the same treatment arm with observations of the primary endpoint. This assumption will be investigated in a sensitivity analysis.

The primary endpoint will be analysed by means of a negative binomial (NB) regression model with the number of asthma exacerbations as the response variable, treatment group, age group (<12 years/ $\geq$ 12 years) and region as fixed effects, and the logarithm of the time in period 4 (in years) as an offset value.

The between treatment group comparison will be performed using a Log Likelihood Ratio (LR) test derived from the NB regression analysis. The null hypothesis is that the rate of clinically relevant asthma exacerbations is equal for the active group and the placebo group. The alternative hypothesis is that the rate of clinically relevant asthma exacerbations is different for the active

Type of document Document ID	Date: Version:	11-Aug-2022 4.0	
	Status:	Final	
	гауе.	310179	

group and the placebo group. The main outcome is the resulting p-value from the LR test reported together with the ratio of the rates and Wald 95% confidence intervals.

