#### 4.6.2 Subgroup analyses

Subgroup analyses are performed to evaluate the consistency of the primary efficacy result across different relevant subgroups. Subgroup analyses of the rate of clinically relevant asthma exacerbations during the efficacy evaluation period (period 4) include:

- age group at randomisation (5-11,12-17 years)
- sex
- race (caucasian, non-caucasian)

Type of document	Date:	11-Aug-2022	
Document ID	Version:	4.0	
	Status:	Final	
INTERNAL USE	Page:	41 of 79	•••••

- asthma background treatment (ICS, ICS plus LABA)
- allergen sensitivity (HDM only, HDM + others)
- geographic region (US, Europe)

The trial is not powered to detect a treatment effect within a subgroup and the subgroup analyses will thus only be descriptive in nature.

A forest plot will be provided by the above specified subgroups. The plot will display the estimated ratio of rates to placebo (and corresponding confidence interval) for each subgroup. The same NB regression model as in the primary efficacy analysis will be applied for the subgroup analyses based on all observed data in FAS corresponding to the primary estimand. The subgroup analyses will be performed using the statistical model for the primary analysis with the inclusion of the subgroup analysed and an interaction with treatment.

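### Baseline ICS level decides which primary-endpoint criteria a subject can meet, but it is missing from the primary model and from the planned subgroups

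*Protocol*

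**What the plan says.** Inclusion criterion I5 admits subjects on low-dose ICS plus LABA, or on medium- or high-dose ICS with or without LABA. Protocol 8.3 and 11.16 bar one of these groups from one treatment step: "Subjects that receive high dose ICS as background treatment are not allowed to double the dose of ICS". That step is also the first of the four alternative criteria for a primary event in SAP 1.1.5: "Doubling of ICS dose compared to background treatment". The other three (at least 3 days of systemic corticosteroids, an emergency room visit, or hospitalisation, the last two requiring systemic corticosteroids) are the criteria for a severe exacerbation. Neither document adapts the definition for high-dose subjects.

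The primary model in SAP 4.2.3 is a negative binomial regression "with the number of asthma exacerbations as the response variable, treatment group, age group" and region, with log time as offset. Randomisation controls age group only: "No other stratification will be used in this trial" (SAP 1.2.3). Protocol 15.12 lists an asthma-treatment subgroup without levels. SAP 4.6.2 sets the levels by LABA use: "asthma background treatment (ICS, ICS plus LABA". ICS use is otherwise only summarised at baseline (SAP 6.2).

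**The concern.** The same composite has a different threshold by baseline dose. A moderate worsening in a subject on low- or medium-dose ICS can be scored as a doubling. In a high-dose subject it counts only if it meets a severe criterion. This is known at randomisation and follows from the protocol's own rules.

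Two things are at stake. The first is precision: if high-dose subjects have a lower countable rate, that difference goes into the dispersion parameter. Precision is scarce here, because SAP 5.1 reports 81% power at 900 subjects from the first reassessment and SAP 1.2 reports 533 randomised. The second is interpretation: the subgroup meant to show consistency by background treatment mixes high-dose subjects into both of its levels, so no planned output shows the primary effect by dose level.

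**Working it through.** **1. The plan's own figure.** Inputs from Protocol 15 and 15.1:
- tests "use a significance level of 5% and all tests and confidence intervals are two-sided"; power 90%;
- placebo rate: "the rate of clinically relevant asthma exacerbations is expected to be approximately 1.4 exacerbations per subject per year", from 0.64 per 24 weeks, so μ1 = 0.64 × 86/24 = 2.29 over 86 weeks;
- rate ratio (RR) 0.70, k = 0.7.

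N per arm = {(1.282 + 1.960)/ln(1/0.7)}² × {1/μ1 + 1/μ2 + 2k} = 82.6 × 2.459 = 203. With a rate of exactly 1.4 it is 202.3. Table 13 gives 202, so the figure reproduces. With 300 × 0.7 = 210 evaluable per arm, power is 90.9%.

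**2. Assumed inputs.** The documents give neither f, the high-dose share, nor s, the share of their otherwise countable events that is lost. Both are assumptions below. High-dose subjects are otherwise given the same underlying rate, which is also an assumption.

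**3. Size of the effect on precision.** Heterogeneity added by the mix = f(1−f)s²/(1−fs)². At f = 0.2, s = 0.5: 0.2 × 0.8 × 0.25/0.81 = 0.049. Added to k, it raises the bracket by 2 × 0.049 = 0.099:
- at μ1 = 2.29: 0.099/2.46 = 4.0%;
- at a lower assumed mean of 0.6 events: 0.099/5.45 = 1.8%.

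For f from 10% to 30% and s from 30% to 70%, the same formula gives 0.3% to 13%. At s = 0 it gives zero.

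This is a simple approximation. A direct comparison takes k = 0.7 as the within-group value. Without adjustment, the rate falls by the factor 1−fs and k becomes 1.7 × {(1−f) + f(1−s)²}/(1−fs)² − 1. With adjustment, the information from the two dose levels is added. Power at 210 per arm, RR 0.70:

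| f | s | k unadjusted | Power, unadjusted | Power, adjusted |
|---|---|---|---|---|
| any | 0 | 0.70 | 90.9% | 90.9% |
| 0.1 | 0.25 | 0.71 | 90.4% | 90.6% |
| 0.2 | 0.5 | 0.78 | 87.7% | 89.2% |
| 0.3 | 0.5 | 0.82 | 86.0% | 88.2% |
| 0.5 | 0.75 | 1.31 | 70.1% | 79.8% |

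At f = 0.2, s = 0.5 the bracket is 2.74 unadjusted and 2.62 adjusted, a 4.9% difference, close to the simple figure. The rest of the fall from 90.9% comes from fewer countable events, and a covariate cannot recover it.

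**4. Bias and type I error.** In simulations of 400 trials per setting, with the likelihood ratio test and no adjustment, the mean RR was 1.00 and 0.70 (true 1.00 and 0.70) at f = 0.3, s = 0.5. It was 1.02 and 0.70 at f = 0.5, s = 0.75. Rejection under the null was 2.5% with no mix, 4.5% and 6.8%, with a Monte Carlo standard error of about 1.1 points.

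**5. Chance imbalance.** At f = 0.2, the SD of the between-arm difference in high-dose share is √(2 × 0.2 × 0.8/210) = 0.039. One SD moves log RR by 0.039 × 0.5/0.9 = 0.022, about 2%, against a standard error of √(2.459/210) = 0.108.

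**6. Age and dose category.** Budesonide DPI counts as high above 400 µg at 5-11 years (Table 3) and above 800 µg from 12 (Table 4). Fluticasone propionate (above 500 µg) and ciclesonide (above 320 µg) have the same high-dose limit in both tables. If ages are even across the 45% aged 5-11 and treatment averages 27 months, 0.45 × 2.25/7 = 14% of subjects turn 12. Only those whose dose is high in Table 3 but not in Table 4 change category. If 20% are high-dose, that is at most 14% × 20%, about 3%.

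**The case against.** The strongest reply is that little may be lost. Protocol 11.16 offers systemic corticosteroids as the alternative to doubling, and at least 3 days of them scores as a primary event. If every worsening barred from doubling is captured that way, power is unchanged. This stands: zero is a possible value, and the documents cannot exclude it.

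Second, k = 0.7 may already contain this mix, since nothing says that it excludes variation by baseline treatment. The first reassessment also estimated dispersion from the trial's own blinded data. This stands against reading the loss as a shortfall in the planned sample size. It does not remove the gain from conditioning on a known factor.

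Third, the rate of severe exacerbations and the times to first and recurrent severe exacerbation (SAP 1.1.7, 4.3.2.2) use only criteria open to every subject. They are a real check on the effect on severe events. They pool all dose levels, however, so they do not show the primary effect in high-dose subjects.

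Fourth, the subgroup analyses are descriptive and unpowered by the SAP's own statement. That limits what a new row can prove, but not the value of splitting by the factor that changes the endpoint.

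Finally, fixing the category at randomisation sets the analysis label only. It does not settle which age governs the doubling rule in practice. If that follows current age, the label will misclassify the few subjects who change category. The two matters are therefore kept separate below.

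**Conclusion.** The point holds as a gap in the analysis plan that is cheap to close. Under protocol compliance, baseline ICS level determines which criteria a subject can meet, and no planned efficacy analysis conditions on it or displays it. SAP 7.1.1.1 takes whichever criterion is recorded on the adverse event form, so a doubling in breach of protocol would still count.

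The loss of effective sample size is zero if all such worsenings are captured through systemic corticosteroids. It is about 2-4% at an assumed 20% high-dose share with half their events lost, and larger at higher assumed values. Both inputs are assumptions.

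Four stronger readings are not supported:
- **The primary comparison is biased or the test invalid.** Allocation is randomised, simulated rate ratios stay near their true values, and a one-SD imbalance moves the ratio about 2% against a standard error of about 11%.
- **High-dose subjects cannot reach the endpoint.** Three of the four criteria remain open to them.
- **The plan never tests the effect on severe events.** It does, in its secondary analyses.
- **The age question touches 14% of subjects.** That counts everyone who turns 12. Those whose category changes are about 3% at most if 20% are high-dose.

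**What to change.** Before unblinding:

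1. In SAP 4.2.3 and the code in 7.2.5, add baseline ICS level (high versus not high) as a fixed effect in the primary negative binomial model. Define it once, from dose and age at randomisation using Protocol Tables 3 and 4.
2. In SAP 4.6.2, add the same two-level factor as a descriptive subgroup beside the LABA split.

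The cost is one degree of freedom, one forest-plot row and a short change to SAP wording. The dose data are already collected for I5.

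Separately, Protocol 8.3 and 11.16 and Tables 3 and 4 should be reconciled, so that it is clear which age governs the doubling rule for a subject who turns 12 during the trial. That is a clarification for the sponsor, and no change to the clinical rule is proposed here.

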11.17 Assessment of symptoms

Rhinoconjunctivitis and asthma symptoms will be recorded in the eDiary by the subject with assistance from his/her caregiver at specified periods during the trial. A video with information on the rating will be available for the subjects.

A total of 10 symptoms; 6 rhinitis and/or conjunctivitis symptoms and 4 asthma symptoms will be measured on a scale from no symptoms to severe symptoms (for details, please see Table 10 and Table 11).

The subject should be instructed in the symptom score using the following definitions:

Confidential		
TPL45489		
Signature:	OnPaper	

Table 10	Subje	ct's symptom scoring

Scored by subject	Definition of score	Numerical Score ¹
No symptoms	No sign/symptom evident	0
Mild symptoms	Symptom clearly present, but minimal awareness; easily tolerated	1
Moderate symptoms	Definite awareness of symptom that is bothersome but tolerable	2
Severe symptoms	Symptom that is hard to tolerate; causes interference with activities of daily living and/or sleeping	3

¹ Scoring scales are not seen by the subjects

Table 11 Construction of symptom scores¹

Rhinitis symptoms	Rhinitis DSS	Rhinoconjunctivitis DSS	Asthma DSS
Runny nose	0-3	0-3	
Blocked nose	0-3	0-3	
Sneezing	0-3	0-3	
Itchy nose	0-3	0-3	
Conjunctivitis symptoms			
Gritty feeling/red/itchy eyes		0-3	
Watery eyes		0-3	
Asthma symptoms			
Chest tightness			0-3
Wheezing			0-3
Cough			0-3
Shortness of breath			0-3
Total range	0-12	0-18	0-12

¹ Scoring scales are not seen by the subjects

11.18 Medication assessment

All subjects are provided with open-label rescue medication for treatment of rhinitis, conjunctivitis and asthma. Use of rhinoconjunctivitis and asthma rescue medication will be recorded by the subject with assistance from his/her caregiver on a daily basis during eDiary periods. The use of asthma background treatment will also be recorded.

Subjects are instructed to report their use of specific rhinoconjunctivitis or asthma rescue medication via the daily eDiary in the baseline period (period 2) and at specified timepoints during the trial. To transform the amount of rhinoconjunctivitis rescue medication used into medication scores the scoring principles detailed in Table 12 will be used.

Table 12	Scoring of rhinoconjunctivitis rescue medication
----------	--

Rescue medication	Subject dosing instruction	Score/ Dose unit ¹	Maximum daily score	
Rhinitis medication score				
Desloratadine tablets ² , 5 mg	< 6 years old: 2.5 ml once daily	4	4	
-	6-11 years old: 5 ml once daily			
Desloratadine Oral solution 0.5 mg/ml	Above 12 years: 1 tablet or 10 ml solution once daily			
Mometasone furoate nasal spray, 50 μg/dose	<12 years old: 1 puff in each nostril once daily	4	8	
	>12 years: 2 puffs in each nostril once daily	2		
Maximum daily rhinitis medication score ³			12	
Conjunctivitis medication score				
Desloratadine tablets ² , 5 mg	5 years old: 2.5 ml once daily	2	2	
Or	6-11 years old: 5 ml once daily			
Desloratadine Oral solution 0.5 mg/ml	Above 12 years: 1 tablet or 10 ml solution once daily			
Azelastine eye drops, 0.5 mg/ml	1 drop in each eye twice daily	1.5	6	
Maximum daily rhinoconjunctivitis medication score ³			20	

¹ Scoring scales are not seen by the subjects

² Desloratadine will count 4 in the rhinitis score and 2 in the conjunctivitis score, based on assumed equal efficacy of antihistamine on the 4 nasal symptoms and 2 eye symptoms (Salmun & Lorber 2002)

³ If any subject exceed the recommended daily dose of symptomatic medication, the actual score will be used

11.19 Asthma Action Plan

An Asthma Action Plan will be given to the subjects and parents/caregivers to provide guidance to effectively manage the subject's symptoms, as recommended by clinical practice guidelines. Subjects will be trained in their Asthma Action Plan by the investigator or designee. According to the Asthma Action Plan, subjects must contact the investigator when asthma symptoms increase or in cases with reduction in lung function. Signs and symptoms of asthma worsening include:

- Cough, wheeze, chest tightness or shortness of breath, or
- Waking at night due to asthma, or
- Can do some, but not all, usual activities, or
- Increased need for reliever medication, or
- Peak flow 50-79% of personal best

The investigator or designee will fill in the appropriate treatment for the subjects in the Asthma Action Plan.

The subject is instructed to call an ambulance while taking reliever medication at regular intervals as pre-specified by the investigator for serious situations when the subjects experience that:

- Symptoms worsens very quickly
- Wheeze, chest tightness or shortness of breath continue after taking reliever medication, or
- There is severe shortness of breath, inability to speak comfortably, blueness of lips, or
- Peak flow is below 50% of personal best

